We will implement a Vascular Access Navigation and Education Quality Improvement Program in the Geisinger Danville, PA chronic kidney disease clinic among individuals with advanced CKD who are nearing dialysis. The Program addresses both care process and patient-level barriers to AV access creation prior to hemodialysis initiation. The program includes: 1) vascular access care navigation, 2) vascular access education, 3) needs and barriers assessment, 4) peer mentoring, and 5) an electronic health record dashboard to track patient progress through the vascular access placement process.

STUDY OBJECTIVE

The overall objective of the Quality Improvement Program is to assess the feasibility, acceptability, and capacity to improve AV access care process confidence and knowledge and potential to yield improvements in pre-emptive AV access creation. This protocol pertains to the research portion of the Quality Improvement Program. The objective of the research portion is to evaluate the Quality Improvement Program's effect on patient's vascular access knowledge and confidence and providers' confidence helping patients navigate vascular access-related care processes.

SPECIFIC AIM AND HYPOTHESES

Specific Aim 1: Evaluate the Vascular Access Navigation and Education Quality Improvement Program's effect on patient vascular access knowledge by comparing pre- and post-program scores on a vascular access questionnaire. *We hypothesize that patient vascular access knowledge will improve pre- to post-program.*

Specific Aim 2: Evaluate the Vascular Access Navigation and Education Quality Improvement Program's effect on patient vascular access confidence (self-efficacy) by comparing pre- and post-program scores on the Self-Efficacy for Managing Chronic Disease questionnaire (adapted to be specific to vascular access). *We hypothesize that patient vascular access confidence will improve pre- to post-program.*

Specific Aim 3: Evaluate the Vascular Access Navigation and Education Quality Improvement Program's effect on providers' confidence helping patients navigate vascular access-related care processes by comparing pre- and post-program scores on a provider vascular access confidence questionnaire. *We hypothesize that provider confidence helping patients navigate vascular access-related care processes will improve pre- to post-program.*

SUBJECT SELECTION

Inclusion Criteria

Patients

- 1) Receive care at the GHS Danville Nephrology Clinic
- 2) Age ≥ 18 years
- 3) eGFR ≤ 25 mL/min/1.73m² and 2-year kidney failure risk $> 10\%$ (depending on sample size and data distribution) based on the Kidney Failure Risk Equation, or nephrologist recommendation for vascular access
- 4) Participation in the Vascular Access Navigation and Education Quality Improvement Program

Providers

- 1) In a professional role involved in hemodialysis vascular access care or process at Geisinger Danville Nephrology Clinic or associated Vascular Surgery, Transplant Surgery, and Radiology Clinics

Exclusion Criteria

Patients

- 1) Too far into the AV access creation process to benefit from the pilot intervention (e.g. completed vascular access surgery appointment or has a surgery appointment scheduled within the next 4 weeks)
- 2) Inability to consent, or
- 3) Inability to complete interviews in English

Providers

- 1) None

Source and Recruitment

Source:

Patients: Up to 40 advanced chronic kidney disease patients meeting selection criteria will be recruited from the Geisinger Health Systems Danville Nephrology Clinic.

Providers and personnel: 30-40 providers and staff involved in AV access creation (nephrologists, vascular surgeons, interventionalists, vascular access navigator, and clinic nurses, managers and schedulers) will be recruited from the Danville Nephrology Clinic and associated Vascular Surgery, Transplant surgery, and Radiology Clinics.

Recruitment:

Patients: Geisinger nurses serving as the Vascular Access Navigators in the Danville Nephrology Clinic will enroll eligible patients into the Vascular Access Navigation and Education Quality Improvement Program using a program-developed GHS chronic kidney disease patient registry. Of those patients who are enrolled into the Quality Improvement Program, the Vascular Access Navigators will query interest in participating in the Aim 4 research study and request patient permission to be contacted by research staff for recruitment.

Geisinger research staff will contact potentially eligible patient participants by telephone, in-person at a previously scheduled, routine clinical appointment using a prepared script, or through a mailed pre-notification letter.

Provider Participants: Eligible providers will be identified by the medical director of the GHS Danville Nephrology Clinic and other GHS nephrologists and vascular surgeons and invited to participate by trained GHS research staff. Recruitment will be performed over the telephone, in person, or by email by trained GHS research staff and will not interrupt work duties or patient care.

Research staff will obtain verbal consent via telephone for research study surveys when preferred by the provider or patient. For in-person program survey participants, additional study information can be found in the written informed consent forms.

SUBJECT ENROLLMENT

Informed Consent Process

Trained study staff at Geisinger will obtain verbal consent over the telephone or written consent in-person prior to enrolling participants in the study. For both in-person and telephone consent, the consent process will be reviewed and all will be allowed to ask questions, request time to consider, and refuse at any time prior to or post consent. For verbal consent over the telephone, the date and name/initials of the research staff member obtaining consent will be documented in the study database.

Geisinger trained research staff obtaining consent will take as much time as needed to explain the study to the participants and answer any questions. Geisinger trained research staff will be available workday/weekend hours to answer any questions. Any voice mail messages or emails will be returned in a timely manner. Participants will be told they are not required to take part in the study and are offered an opportunity to refuse at any time. Participants are also advised they can stop their participation in the study at any time. They are also told their participation will not affect their care or employment.

STUDY PROCEDURES

Research Design

Consented patient and provider participants will complete questionnaires before and after program implementation. We will use a pre- and post-assessment design to evaluate the primary and secondary outcomes. We will collect patient and provider data via questionnaires.

Sample Size

We will recruit up to 40 patients and 30-40 providers and staff.

Study procedures

GHS trained research staff will administer questionnaires to patient and provider/clinic personnel participants. We will obtain verbal or written informed consent prior to enrolling participants in the study. Following screening, recruitment and consent procedures, trained GHS research staff will administer pre-implementation questionnaire questions to participating patients in person (at a previously scheduled, routine clinical appointment or at a time and location of their choosing) or over the telephone (**Appendix A**). Questionnaire administration will not disrupt routine clinical care. Similarly, following screening, recruitment and consent procedures, trained GHS research staff will administer the pre-implementation questionnaire questions to participating providers and clinic personnel at a time that does not interfere with their professional duties in person or over the telephone (**Appendix B**).

The patient and provider/clinic personnel questionnaire questions will take approximately 10 minutes to complete. For both telephone and in person administration of the questionnaires, interviewers will read the questions exactly as written and the response choices for each question. Participants may refuse to answer any question(s). The number of incomplete questionnaires will be monitored.

Patient and provider/personnel participants will also be asked to complete a demographic card (**Appendices C & D**). Patient demographic information collected will include: sex, age, race, ethnicity, education level, and income level. Provider/personnel demographic information collected will include: sex, age, race, ethnicity, professional role, time worked in role at Geisinger and total, and time worked with chronic kidney disease patients, dialysis patients, and with patients going through the vascular access creation process.

At the conclusion of the quality improvement program, trained GHS research staff will administer the post-implementation questionnaire questions to participating patients in person (at a previously scheduled, routine clinical appointment or at a time and location of their choosing) or over the telephone and to participating providers/clinic personnel at a time that does not interfere with their professional duties in person or over the telephone. Questionnaire administration will not disrupt routine clinical care.

Remuneration

There will be no cost to study participants. Patient participants will receive \$25 total remuneration for pre- and post-implementation questionnaires. Participants electing to terminate the questionnaire early will receive the full amount. A \$10 gift card will be given to patient participants for pre-implementation questionnaires, and a \$15 gift card will be given to patient participants for post-implementation questionnaires. A compensation letter will accompany the remuneration.

DATA ANALYSIS AND POWER

Data Collection Variables

See research pre-/post-intervention questionnaires for data collected from patient and providers (**Appendices A & B**).

Data Collection

Table 1 provides an overview of the data to be collected. The outcomes are patient and provider vascular access-related confidence (self- efficacy) and patient vascular access knowledge. Patient confidence will be evaluated using a questionnaire with 11 total items (3 research team-developed questions and 8 Perceived Kidney Disease Self-Management Scale questions (a validated scale).(7) Patient knowledge will be evaluated using an 8-item research team-developed questionnaire. Provider confidence will be evaluated by an 11-item research team-developed questionnaire.

Table 1. Data Collection Variables.

Outcomes	Pre-Implementation	Post-Implementation
Patient confidence navigating the vascular access creation process (self-efficacy)	X	X
Patient vascular access knowledge	X	X
Provider confidence helping patients navigate the vascular access creation process (self-efficacy)	X	X
Demographics		
Patient age, sex, ethnicity, race, education level, income level	X	
Provider age, sex, ethnicity, race, professional role, time worked in role at GHS and total, and time worked with CKD patients, dialysis patients, and patients going through the vascular access creation process	X	

Data Analysis

Pre- and post-implementation confidence and knowledge measures scores will be calculated according to measure scoring instructions (kidney disease self-management: mean of 8 items,(7) patient vascular access process confidence: mean of 3 items, patient vascular access knowledge: mean of 8 items, provider confidence: mean of 11 items). We will use a paired sample student's t-test to compare pre and post-test score means. Analyses will be performed in SAS v9.4 and R v3.3.2 or later.

RISKS AND DISCOMFORTS

The research poses no more than minimal risk to the participants. Participants will be told that if they want their participation dropped from the study, the researchers will do so at any time, and that if they change their mind about participating in the study, they can stop at any time. Participants will be told they will not have any change in the medical care they receive (patients) or their employers (providers/staff) and that their information will not be released to their physicians, employers, health care organization, or any other party without their permission.

In-person appointments for questionnaire completion will be optional. In cases where a participant chooses to participate in an in- person questionnaire, written informed consent will be obtained at the time of the encounter. In cases where a participant prefers to participate in an over-the-telephone questionnaire, verbal consent will be obtained.

The main risk is loss of privacy or confidentiality. There is minimal risk of loss of confidentiality associated with participating in any study. Every effort will be made to protect patient and staff confidentiality. Participants will be told we will do all we can to keep their information private. But this cannot be guaranteed and that their personal information may be disclosed if required by law. Participant concerns about confidentiality will be addressed by the following safeguards. The nature of the project and its associated risks and benefits will be explained fully to all participants at the time of recruitment and again at the time of the questionnaire administration. No individual will be subjected to any pressure to participate or to answer any questions they may not wish to answer. Participants may stop the questionnaire at any time without sustaining adverse consequences.

There is minimal risk of emotional distress. The risk is minimal, however, as the issues covered in the questionnaires are issues often discussed during the course of routine clinical care. There is minimal risk of distress when discussing the AV access placement process. However, licensed social workers and physicians employed by the GHS Danville Nephrology Clinic will be available to participating patients if fears or concerns are uncovered.

POTENTIAL BENEFITS

Individual: There are minimal anticipated direct benefits to the subjects participating in this study. However, participation will provide patients and providers an opportunity to discuss their experience with the vascular

access creation process in a supportive environment. The topics discussed may increase patient interest and engagement in their own care, and provider interest and engagement in the vascular access creation process. Participants will be told that they are helping researchers and Geisinger Health System develop ways to improve the care of patients with kidney disease.

Society: The study will provide critical knowledge on the effectiveness of integrated health system quality improvement initiatives to improve the care and clinical outcomes of patients with kidney disease. If we find the quality improvement initiative is effective, it will provide a model for other health systems to implement. In particular, we will identify ways to implement effective health system tools to inform patient centered kidney transitions care, and we will identify ways to implement care management and behavioral programs that will improve patients' transitions to kidney failure.

MONITORING AND QUALITY ASSURANCE

Eligible participants' information will be kept private and data secure. We will only utilize PHI that is absolutely necessary for our identification of potential participants' eligibility for the study. Our study staff are trained in research ethics and HIPAA privacy compliance. Study participants' information will not be released to their physicians, employers, health care organization, or any other party without the participants' permission. PHI will not be used or disclosed to any other person or entity, except as required by law, for authorized oversight of the research study.

All hardcopy study data will be stored in locked file cabinets within research offices and not the clinical sites, as well as on secure servers where only study staff have access. No personal identifiers, such as participant names, are being collected. All paper and electronic documents will be identified with a unique study ID. All paper documents containing study IDs will be shredded after they are scanned, and saved on the secure server. All responses will be kept confidential and stripped of participant identifiers other than unique study IDs.

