Appendix A. Patient Pre-Implementation & Post-Implementation Questionnaires

[Interviewer reads each question and answer options to the participant, and records their response on this document. Interviewer can repeat questions and answer options as needed, and answer participants' general questions, but should not provide additional information that would alter the participant's response.]

1.1 Perceived Kidney Disease Self-Management Scale + Self-efficacy Scale for Vascular Access Process

We would like to know how much you agree or disagree with the following statements about your kidney disease. For each statement, please choose a number between 1 (strongly disagree) and 5 (strongly agree).

1. It is difficult for me to find effective solutions to problems that occur with managing my kidney disease.
a. Choices: 1 2 3 4 5
 Strongly disagree Somewhat disagree Neutral Somewhat agree Strongly agree

2. I find efforts to change things I don't like about my kidney disease are ineffective.
a. Choices: 1 2 3 4 5
 Strongly disagree Somewhat disagree Neutral Somewhat agree Strongly agree

3. I handle myself well with respect to my kidney disease.
a. Choices: 1 2 3 4 5
 Strongly disagree Somewhat disagree Neutral Somewhat agree Strongly agree

4. I am able to manage things related to my kidney disease as well as most other people.
a. Choices: 1 2 3 4 5
 Strongly disagree Somewhat disagree Neutral Somewhat agree Strongly agree

5. I succeed in the projects I undertake to manage my kidney disease.
a. Choices: 1 2 3 4 5
 Strongly disagree Somewhat disagree Neutral Somewhat agree Strongly agree

6. Typically, my plans for managing my kidney disease don't work out well.
a. Choices: 1 2 3 4 5
 Strongly disagree Somewhat disagree Neutral Somewhat agree Strongly agree

7. No matter how hard I try, managing my kidney disease doesn't turn out the way I would like.
a. Choices: 1 2 3 4 5
 Strongly disagree Somewhat disagree Neutral Somewhat agree Strongly agree

8. I'm generally able to accomplish my goals with respect to managing my kidney disease.
a. Choices: 1 2 3 4 5
 Strongly disagree Somewhat disagree Neutral Somewhat agree Strongly agree

We would like to know how confident you feel about things involved with getting a dialysis vascular access. For each question, please give an answer between 1 and 10, where 1 is “not at all confident”, and 10 is “totally confident”.

1. How confident do you feel completing the steps involved in getting a dialysis vascular access?

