1.2. Vascular Access Knowledge Questionnaire

We would like to understand what you know about vascular access. Please answer the next questions the best you can based on what you know now.

1. What does a vascular access do? [*correct answer=it makes a way for your blood to get to the hemodialysis machine*]
 - a. It helps you figure out what you can eat and drink when you start hemodialysis
 - b. It makes a way for your doctor to know how well your kidneys are doing
 - c. It makes a way for your blood to get to the hemodialysis machine
 - d. Don't know

2. What are the 3 kinds of vascular access for hemodialysis? [*correct answer= fistula, graft, catheter*]

[Interviewer asks participant to name the 3 kinds of vascular accesses. Interviewer does not read off the response options. Interviewer records participant's responses below by circling each of the vascular accesses they name correctly, and writing any incorrect responses under "other".]

- a. Fistula
 - b. Graft
 - c. Catheter
 - d. Other: _____
 - e. Don't know
-
3. What kind of vascular access can get infected most easily? [*correct answer= catheter*]
 - a. Fistula
 - b. Graft
 - c. Catheter
 - d. Don't know

4. What kind of vascular access usually lasts the longest? *[correct answer= fistula]*
 - a. Fistula
 - b. Graft
 - c. Catheter
 - d. Don't know

5. Who picks the kind of vascular access and where it will go on the body? *[correct answer= kidney doctor, patient, and surgeon together]*
 - a. Kidney doctor only
 - b. Patient only
 - c. Surgeon only
 - d. Kidney doctor, patient, and surgeon together
 - e. Don't know

6. Vein mapping helps you figure out the best place on your body for your access. *[correct answer= true]*
 - a. True
 - b. False
 - c. Don't Know

7. Vein mapping happens after vascular access surgery. *[correct answer= false]*
 - a. True
 - b. False
 - c. Don't Know

8. A fistula is ready to be used for dialysis (in other words, ready to be stuck with a needle for dialysis) within one week after it is made. *[correct answer= false]*
 - a. True
 - b. False
 - c. Don't Know

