1.1. Vascular Access Confidence Questionnaire

We would like to know how confident you feel about the dialysis vascular access creation process. For each question, please give an answer between 1 and 10, where 1 is “not at all confident”, and 10 is “very confident”.

1. How confident are you in doing your part to assist your patients through the vascular access creation process?
 - a. Choices: 1.....2.....3.....4.....5.....6.....7.....8.....9.....10
Not at all Somewhat Very

2. How confident are you in knowing how far your patients have progressed in the vascular access creation process?
 - a. Choices: 1.....2.....3.....4.....5.....6.....7.....8.....9.....10
Not at all Somewhat Very

3. How confident are you in your own understanding of the vascular access creation steps?
 - a. Choices: 1.....2.....3.....4.....5.....6.....7.....8.....9.....10
Not at all Somewhat Very

4. How confident are you in your ability to explain vascular access to your patients?
 - a. Choices: 1.....2.....3.....4.....5.....6.....7.....8.....9.....10
Not at all Somewhat Very

5. How confident are you in your ability to explain the vascular access creation process to your patients?
 - a. Choices: 1.....2.....3.....4.....5.....6.....7.....8.....9.....10
Not at all Somewhat Very

6. How confident are you in your ability to help your patients overcome barriers to vascular access creation?
 - a. Choices: 1.....2.....3.....4.....5.....6.....7.....8.....9.....10
Not at all Somewhat Very

7. How confident are you in your ability to communicate with your patients about their emotions surrounding the vascular access creation process?
 - a. Choices: 1.....2.....3.....4.....5.....6.....7.....8.....9.....10
Not at all Somewhat Very

8. How confident are you in communicating appropriate and timely information to other providers about your patients who are going through the vascular access creation process?

a. Choices: 1.....2.....3.....4.....5.....6.....7.....8.....9.....10
Not at all Somewhat Very

9. How confident are you that you are receiving appropriate and timely information from other providers about your patients who are going through the vascular access creation process?

a. Choices: 1.....2.....3.....4.....5.....6.....7.....8.....9.....10
Not at all Somewhat Very

10. How confident are you that you are giving your patients the educational materials and information they need to get through the vascular access creation process?

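### Interview mode may differ between pre and post and is not listed as recorded, and only a soft cue asks patients to answer the knowledge items unaided

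*Protocol*

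**What the plan says.** **Mode.** Study procedures describes the patient interview before the program in these words: "administer pre-implementation questionnaire questions to participating patients in person (at a previously scheduled, routine clinical appointment or at a time and location of their choosing". The telephone is the stated alternative. Afterwards they will "administer the post-implementation questionnaire questions to participating patients in person (at a previously scheduled, routine clinical appointment", with other places and the telephone again allowed. Providers and clinic staff also have both options at both times. Risks and Discomforts leaves the choice to the participant: "In-person appointments for questionnaire completion will be optional".

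**Standardisation.** "For both telephone and in person administration of the questionnaires, interviewers will read the questions exactly as written". Appendix A adds that the interviewer "should not provide additional information that would alter the participant's response".

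**Knowledge items.** Appendix A section 1.2 opens with "Please answer the next questions the best you can based on what you know now". For item 2, which asks for the three kinds of access, "Interviewer does not read off the response options".

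**Data and analysis.** Table 1 lists outcomes and demographics only. The questionnaires and demographic cards contain no mode field. The Data Analysis section and the SAP both specify a paired t-test with no comparison group and no reference to mode.

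**The concern.** A paired t-test removes stable differences between people. It does not remove a change in how the same person was measured. With no control group, any systematic shift in measurement conditions between pre and post goes straight into the estimated change.

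Two routes are open.

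- **Look-up.** The knowledge questionnaire is a factual test with right answers. The program delivers education, so a patient may have something to consult at post that was not there at pre. This affects Aim 1 and would push the score upwards.
- **Mode.** A participant seen in clinic at one interview and telephoned at the other adds any mode effect to the change score. This could touch all three aims, in either direction.

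If mode is not recorded when the interview takes place, the second route may be impossible to examine later.

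**Working it through.** The plan gives no figure to reproduce: no significance level, effect size or SD of change. The procedural point is settled by reading; the numbers below only illustrate scale.

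**1. What the safeguards cover.**

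| Safeguard | Covers | Leaves open |
|---|---|---|
| Same script in both modes (Study procedures) | Wording of questions | Setting, and what the patient can see |
| Limit on interviewer input (Appendix A) | What the interviewer says | What the patient consults |
| Opening sentence of section 1.2 | Asks for present knowledge | Notes, handouts, help from others |

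Item 2 is the most exposed, since it is unaided recall and could be answered from a page. One small conflict also needs reconciling: Study procedures has response choices read for every question, while item 2 says they are not read.

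**2. Look-up (Aim 1).**

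From the documents: up to 40 patients; knowledge score is the mean of 8 items; paired t-test. Assumed: all 40 complete, items scored 0/1, two-sided 5% level, SD of change s = 0.15, 0.20 or 0.25, no true learning. A fraction f of patients gains k items at post by looking answers up.

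- Mean bias = f × k/8.
- SD of observed change = √(s² + f(1−f)(k/8)²).
- Noncentrality = bias ÷ (SD/√40), compared with a critical t of about 2.02.

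Worked case, f = 0.25, k = 2, s = 0.20: bias = 0.25 × 0.25 = 0.0625. SD = √(0.0400 + 0.1875 × 0.0625) = 0.227. Standard error = 0.227/6.325 = 0.036. Noncentrality = 0.0625/0.036 ≈ 1.74, so the chance of exceeding 2.02 is about 39%. Simulation (20,000 runs per cell) agrees:

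| Patients gaining, items | Mean bias | s = 0.15 | s = 0.20 | s = 0.25 |
|---|---|---|---|---|
| none | 0 | 2.4% | 2.6% | 2.6% |
| 10%, 2 items | 0.025 | 14.4% | 10.6% | 8.3% |
| 25%, 2 items | 0.0625 | 55.2% | 39.0% | 29.1% |
| 50%, 1 item | 0.0625 | 65.5% | 44.8% | 32.1% |
| 50%, 2 items | 0.125 | 97.8% | 90.8% | 78.8% |

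Cells are the chance of a significant result in favour of the program when nothing was learned. For scale, with 40 pairs an observed change is significant from about 0.32 SD.

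**3. Mode switching.**

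Let m be the mode effect, p the share switching in the direction that raises scores and q the share switching the other way.

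- Shift in the mean = m × (p − q).
- Added variance = m² × [(p + q) − (p − q)²].

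Take a 1–10 confidence mean, an assumed SD of change of 2.0 and an assumed m = 0.5, with half the participants switching:

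- p = q = 0.25: shift = 0. Added variance = 0.25 × 0.5 = 0.125, so the SD goes from 2.00 to √4.125 = 2.03.
- p = 0.50, q = 0: shift = 0.5 × 0.5 = 0.25.

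Balanced switching adds a little noise and no bias. Bias needs an imbalance, which the documents neither show nor prevent.

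**4. Reach of a same-mode analysis.** If half switched, 40 × 0.5 = 20 pairs would remain. The standardised change detectable with 80% power would rise from about 0.45 to 0.66. Pairs interviewed by telephone both times stay in this analysis and keep any look-up gain.

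**The case against.** The strongest reply is that this is a small, minimal-risk evaluation in which choice of mode is deliberate, both modes are offered in the same terms at both times, and the script is standardised. All of that stands. It limits the point to a cheap improvement and argues against forcing a mode.

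Several stronger readings are tempting, and the documents do not support them.

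- **That nothing asks patients to rely on their own knowledge.** The opening of section 1.2 does ask for this. What is missing is an explicit instruction or check about materials and help.
- **That patients receive handouts between the interviews.** The protocol lists an education component without describing take-home material. The nearest text is provider item 10, on "giving your patients the educational materials and information they need". That item is asked before implementation too, so it fits materials already used in ordinary care. Patients are also enrolled in the program before being approached for the research, and the timing of any material is not stated.
- **That the problem is specific to the telephone.** In-person interviews may take place wherever the patient chooses, so materials could be at hand there as well.
- **That all three aims are inflated.** Looking up answers does not apply to self-rated confidence. For Aims 2 and 3 only mode switching is relevant. If half of 40 participants all switched the same way, with an upward effect of 0.3, 0.5 or 1.0 points and an SD of change of 2.0, the false-improvement rate would be about 7%, 11% or 32%. Nothing in the documents suggests that one-way pattern or that direction.

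The pre mode may be partly recoverable. Telephone consent is logged in the study database, and Risks and Discomforts pairs verbal consent with telephone questionnaires and written consent with in-person ones. This is an indirect trace, and no routine record of the post mode is described.

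**Conclusion.** The point holds as a minor, inexpensive improvement. The text establishes that mode is free at both interviews, that no rule keeps it the same, that it is not listed as recorded or analysed, and that nothing beyond a soft cue tells patients to answer the knowledge items unaided.

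For Aim 1, an upward bias is plausible if reference material is easier to reach at post. That is an inference from the education component, not something the documents state. For Aims 2 and 3, bias requires systematic switching, and its sign is unknown.

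The size of either effect cannot be derived from the documents. The look-up table shows only that, under its assumptions, a minority of patients gaining two items would be enough to matter. It does not show that they would.

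**What to change.** - **Study procedures:** by default use the pre-interview mode again at post, switching only if the participant would otherwise be missed. Record the mode of each interview in REDCap.
- **Appendix A, section 1.2:** add one scripted line, identical at pre and post and in both modes, asking the patient to answer without notes, written material or help from others. Reconcile the reading rule for item 2 with Study procedures at the same time.
- **SAP:** add a sensitivity paired t-test restricted to same-mode pairs, and state that it addresses mode switching and not look-up. The scripted line is the safeguard against look-up.

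The cost is a mode entry for each interview, one sentence of script and one extra analysis. Scheduling becomes slightly less flexible, and the sensitivity analysis has fewer pairs. The telephone option remains and nobody is excluded.
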